### List of Abbreviations

ADCC	antibody-dependent cellular cytotoxicity
AE	adverse events
ALC	Absolute lymphocyte count
ACTH	Adrenocorticotrophic hormone level
ALT	alanine aminotransferase
ANC	absolute neutrophil count
APC	antigen-presenting cells
AST	aspartate aminotransferase
AUC	area under the curve
BMS	Bristol-Myers Squibb
BORR	best overall/objective response rate
BW	body weight
CBC	complete blood count
CDCC	complement-dependent cellular cytotoxicity
CI	confidence interval
CHO	Chinese hamster ovary cell
CL	systemic clearance
CTLA-4	cytotoxic T lymphocyte antigen 4
cm	centimeter
Cmax	maximum concentration
Cmin	minimum concentration
CMP	comprehensive metabolic panel
COMPTV	center of mass of the planned target volume
CR	complete response
CRF	case report form
CT	computed tomography
CTCAE	Common Toxicity Criteria for Adverse Events
CTV	clinical target volume
DCR	disease control rate
DMSO	dimethyl sulfoxide
DNA	deoxyribonucleic acid
DSMC	Data and Safety Monitoring Committee
DTIC	dacarbazine
ECL	electrochemiluminescent
ECOG	Eastern Cooperative Oncology Group
ESR	expedited safety report
EU	European Union

FDA	Food and Drug Administration
FSH	follicle stimulating hormone
GCP	Good Clinical Practice
g/dL	grams per deciliter
GI	gastrointestinal
g/L	grams per liter
GTV	gross tumor volume
Gy	Gray
HCG	human chorionic gonadotropin
HepB	hepatitis B
HepC	hepatitis C
HIPAA	Health Insurance Portability and Accountability Act of 1996
HIV	human immunodeficiency virus
HLA	human leukocyte antigen
HLA-DR	human leukocyte antigen-disease resistance
hr	hours
HR	high risk
HRT	hormone replacement therapy
IB	investigational brochure
ICH	International Conference on Harmonisation
IDO	indoleamine 2,3-dioxygenase
IEC	International Education Council
IgG1	human immunoglobulin G
IMRT	intensity modulated radiation therapy
IND	investigational new drug
Ipi	ipilimumab
ir	immune-related
irAE	immune-related adverse effects
irBOR	immune-related best overall response
irCR	immune-related complete response
irPD	immune-related progressive disease
irPR	immune-related partial response
irRC	immune-related response criteria
irSD	immune-related stable disease
irSPD	immune-related sum of product diameter
IRB	investigational review board
ITT	insulin tolerance test
ITV	intensive therapy unit
IU/L	International Unites per liter
IV	intravenous

kg	kilogram
L	liter
LDH	lactate dehydrogenase
LFT	liver function test
mAb	monoclonal antibody
mcg/mL	micrograms per milliliter
mg	milligram
mg/dL	milligrams per deciliter
mg/kg	milligrams to kilograms
mg/kg/day	milligrams per kilogram per day
mg/m 	milligrams per metered square
mIU/mL	milli international units per milliliter
mL	milliliter
MLC	multi-leaf collimator
mL/h	milliliters per hour
mL/h/kg	milliliters per hours per kilogram
mL/min	milliliter per minute
mm	millimeter
mmHg	millimeters of mercury
MRI	magnetic resonance imaging
MR	magnetic resonance
mRNAs	micro ribonucleic acids
MV	megavoltage
Mwho	modified World Health Organization
NCA	non-compartmental analysis
NCI	National Cancer Institute
NYHA	New York Heart Association
OAR	organs at risk
OR	overall response
OS	overall survival
OSUCCC	Ohio State University Comprehensive Cancer Center
PAP	
PET/CT	positron emission tomography-computed tomography
PFS	progression-free survival
PHA	
PHI	protected health information
PI	primary investigator
PK	pharmacokinetic
PPK	population pharmacokinetics
PR	partial response

PS	performance status
PSA	prostate-specific antigen
PSMA	prostate-specific membrane antigen
PTV	planned target volume
q3w	every three weeks
RECIST	response evaluation criteria in solid tumors
RP2D	recommended phase II dose
RTOG	Radiation Therapy Oncology Group
SABR	stereotactic ablative radiation therapy
SAE	serious adverse event
SD	stable disease
SPD	sum of the products of diameters
SRS	slow-reacting substance
SUSAR	suspected, unexpected serious adverse reaction
SWOG	Southwest Oncology Group
TA	tumor assessment
TAA	tumor-associated antigen
TMA	tissue microarray
ug/mL	microgram per milliliter
uL	microliter
ULN	upper limit of normal
USP	acetic acid solution
V ss	volume of distribution at steady-state
WBC	white blood cell
WOCBP	women of childbearing potential

## Study Summary

Title	A phase II study using stereotactic ablative radiation therapy (SABR) and ipilimumab in patients with oligometastatic melanoma
Short Title	SABR and ipilimumab in oligometastatic melanoma
Protocol Number	OSU #12182 IRB # 2013C0096
Phase	2
Methodology/Study Design	Phase II, single-arm, open label, non-randomized study with stereotactic ablative radiation therapy and ipilimumab as outlined in the treatment plan. We will perform a phase II trial with a primary endpoint of progression-free survival.
Study Duration	24 months
Study Center(s)	Single center
Objectives	
Primary Objectives:
 
 
To determine the progression-free survival of the combination of SABR and ipilimumab in patients with oligometastatic melanoma using mWHO criteria
 
 
Secondary and Correlative Objectives:
 
 
To determine the progression-free survival of the combination of SABR and ipilimumab in patients with oligometastatic melanoma using irRC criteria
 
To evaluate the tolerability and safety of the combination
 
To evaluate of response rate based on mWHO & irRC criteria
 
To evaluate the local control rate
 
To evaluate the overall survival rate
 
To determine the effect of SABR and ipilimumab on changes in blood and serum markers: absolute lymphocyte count, T-cell activation markers, T-cell suppression markers, T-helper cells and related cytokines, T-reg markers, co-stimulatory molecules, and serum cytokines
 
To determine the association between response, progression-free survival and genomic DNA mutations in key melanoma genes and tumor antigen expression
 

Number of Subjects	32

Diagnosis and Main Inclusion Criteria
	
Male and female patients <math>\geq</math> 18 years old with Stage IV melanoma
 
Key Inclusion Criteria:
 
 
• Confirmed melanoma with metastatic disease confined to an area amenable to SABR (lung, liver, bone, brain, adrenal, nodal station outside the regional lymph drainage of the primary)
 
• 1-3 sites of metastatic disease to be targeted by SABR
 
• Normal end organ function
 
• Measurable disease by CT
 
• ECOG PS of 0 - 2
 


Study Product, Dose, Route, Regimen
	
Ipilimumab will be administered on week 1 at a dose of 3 mg/kg. Subsequent cycles of ipilimumab will be given every three weeks (week 4, 7, & 10).
 
SABR will be delivered between the second and third doses of ipilimumab(week 5-6) using the following suggested schedules: 18 Gy x 3 to lung, 10 Gy x 5 to liver, 6 Gy x 6 to nodal stations, 12 Gy x 3 to adrenal, 18 Gy x 1 to bone, and 24 Gy x 1, 18 Gy x 1, 15 Gy x 1 to < 2.0 cm, 2.0-3.0 cm, and >3 cm brain metastases, respectively.
 
Duration of therapy: Patients will receive at least 12 weeks of therapy and will be observed for toxicity for 90 days after the last ipilimumab infusion. Patients will remain on study until evidence of progression or death.

Duration of administration
	
12 weeks

Reference therapy
	
NA

Statistical Methodology	
Overall, this study will require 32 evaluable patients. We estimate that we will accrue 1-2 patients per month. Thus, the minimum study duration will be 16 months and the maximum is 32 months.
 
Current literature and experience with maintenance therapy in this patient population shows that we can expect that this treatment regimen will not be considered promising in this patient population if at most 15% of patients are progression-free and alive at 6 months. For this agent to be considered promising in this patient population, we would expect an improvement in the 6-month PFS rate to at least 35% with this regimen in this patient population. Constraining the Type I and II error rates to 10% each, a 2-stage phase II Simon minimax study design will require 32 evaluable patients to test these hypotheses regarding the 6-month PFS rate with ipilimumab when given in combination with the stereotactic ablative radiation therapy in this patient population.

----------------------------	---

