#### **4.0 SUBJECT SELECTION AND WITHDRAWAL CRITERIA**

For entry into the study, the following criteria **MUST** be met. Any exceptions from the protocol-specific selection criteria must be approved by the Principal Investigator and/or the Institutional Review Board (IRB) before enrollment.

Patients must have baseline evaluations performed prior to the first dose of study drug and must meet all inclusion and exclusion criteria. Results of all baseline evaluations will be reviewed by the Principal Investigator prior to enrollment, to verify that all inclusion and exclusion criteria have been satisfied. In addition, the patient must be thoroughly informed about all aspects of the study, including the study visit schedule and required evaluations and all regulatory requirements for informed consent. The written informed consent must be obtained from the patient prior to screening procedures being performed. The following criteria apply to all patients enrolled onto the study unless otherwise specified.

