##### **4.1 Inclusion criteria**

- 1) Willing and able to give written informed consent.
- 2)  $\geq 18$  years of age
- 3) ECOG Performance Status 0-2 (see Appendix I)
- 4) Histologic diagnosis of melanoma with metastatic disease to a visceral organ (lung, liver, brain, adrenal, nodal station outside the regional lymph drainage of the primary, vertebral bodies)
- 5) 1-3 sites of metastatic disease able to be targeted by SABR
- 6) Required values for initial laboratory tests:

- WBC  $\geq 2000/\mu\text{L}$
- ANC  $\geq 1000/\mu\text{L}$
- Platelets  $\geq 75 \times 10^3/\mu\text{L}$
- Hemoglobin  $\geq 9 \text{ g/dL}$  ( $\geq 80 \text{ g/L}$ ; may be transfused)
- Creatinine  $\leq 2.0 \times \text{ULN}$
- AST/ALT  $\leq 2.5 \times \text{ULN}$  for patients without liver metastasis,  
 $\leq 5$  times for liver metastases
- Bilirubin  $\leq 2.0 \times \text{ULN}$ , (except patients with Gilbert's Syndrome, who must have a total bilirubin less than 3.0 mg/dL)
- No active or chronic infection with HIV, Hepatitis B, or Hepatitis C.
- Negative Pregnancy test at screening
- WOCBP must have a negative serum or urine pregnancy test (minimum sensitivity 25 IU/L or equivalent units of HCG) within 3 days before the start of ipilimumab.

7.) Women of childbearing potential (WOCBP) and male subjects of fathering potential must be using an adequate method of contraception to avoid pregnancy throughout the study and for up to 3 months after the last dose of investigational product, in such a manner that the risk of pregnancy is minimized.

WOCBP include any female who has experienced menarche and who has not undergone successful surgical sterilization (hysterectomy, bilateral tubal ligation, or bilateral oophorectomy) or is not post-menopausal. Post-menopause is defined as:

- Amenorrhea  $\geq$  12 consecutive months without another cause, or
- For women with irregular menstrual periods and taking hormone replacement therapy (HRT), a documented serum follicle stimulating hormone (FSH) level  $\geq$  35 mIU/mL.

Women who are using oral contraceptives, other hormonal contraceptives (vaginal products, skin patches, or implanted or injectable products), or mechanical products such as an intrauterine device or barrier methods (diaphragm, condoms, spermicides) to prevent pregnancy, or are practicing abstinence or where their partner is sterile (eg, vasectomy) should be considered to be of childbearing potential.

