##### ***Definition of Measurable and Non-Measurable Lesions***

**Measurable Lesions** are lesions that can be accurately measured in two perpendicular diameters, with at least one diameter  $\geq 20$  mm and the other dimension  $\geq 10$  mm (10 mm x 10 mm for spiral CT). The area will be defined as the product of the largest diameter with its perpendicular. Skin lesions can be considered measurable.

**Non-Measurable (evaluable) Lesions** are all other lesions, including unidimensionally measurable disease and small lesions (lesions without at least one diameter  $\geq 20$  mm), and any of the following:

- Lesions occurring in a previously irradiated area (unless they are documented as new lesions since the completion of radiation therapy), bone lesions, leptomeningeal disease, ascites, pleural or pericardial effusion, lymphangitis cutis/pulmonis, abdominal masses that are not pathologically/cytologically confirmed and followed by imaging techniques and cystic lesions.
- All measurable and non-measurable lesions should be measured at screening and at the defined tumor assessment timepoints (see Section 5, Table 2). Extra

assessments may be performed, as clinically indicated, if there is a suspicion of progression.

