**Definition of Overall Response Using irRC**

Overall response using irRC will be based on these criteria: The sum of the products of the two largest perpendicular diameters of all index lesions is measured and captured as the SPD baseline. At each subsequent tumor assessment, the sum of the products of the two largest perpendicular diameters of all index lesions and of new measurable lesions are added together to provide the Immune Response Sum of Product Diameters (irSPD).

**Immune-Related Complete Response (irCR):** Complete disappearance of *all* tumor lesions (index and nonindex together with no new measurable/unmeasurable lesions) for at least 4 weeks from the date of documentation of complete response.

**Immune-Related Partial Response (irPR):** A decrease, relative to baseline of the irSPD compared to the previous SPD baseline, of 50% or greater is considered an immune Partial Response (irPR).

**Immune-Related Stable Disease (irSD):** irSD is defined as the failure to meet criteria for immune complete response or immune partial response, in the absence of progressive disease.

**Immune-Related Progressive Disease (irPD):** It is recommended in difficult cases to confirm PD by serial imaging. Any of the following will constitute progressive disease:

- At least 25% increase in the sum of the products of all index lesions over baseline SPD calculated for the index lesions.
- At least a 25% increase in the sum of the products of all index lesions and new measurable lesions (irSPD) over the baseline SPD calculated for the index lesions.

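### Section 4 drops the synopsis requirement for measurable disease, so patients with no index lesion can enrol and cannot be scored for mWHO partial response or the SPD-based irRC categories

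*Combined protocol and SAP*

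**What the plan says.** **Eligibility.** The Study Summary gives "Measurable disease by CT" among the key inclusion criteria and lists the eligible sites as "lung, liver, bone, brain, adrenal, nodal station outside the regional lymph drainage of the primary". Section 4.0 introduces the operative list with "For entry into the study, the following criteria", followed by a statement that they must be met. Section 4.1 then asks for "1-3 sites of metastatic disease able to be targeted by SABR" and ends its site list with "nodal station outside the regional lymph drainage of the primary, vertebral bodies". Neither 4.1 nor 4.2 mentions measurability. Section 4.2 sets upper limits on lesion size but no minimum.

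**Lesion definitions.** Section 6.10.1 requires one diameter of at least 20 mm and the other of at least 10 mm (10 x 10 mm for spiral CT). Smaller lesions are non-measurable, and so are "bone lesions, leptomeningeal disease, ascites, pleural or pericardial effusion". Index lesions are chosen from measurable lesions only, and baseline SPD is their sum.

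**Scoring.** Under irRC, Section 6.10.3 defines progression as "At least 25% increase in the sum of the products of all index lesions over baseline SPD calculated for the index lesions", or the same increase once new measurable lesions are added. Section 1.5.3 states that irRC rests on the SPD of index and new lesions and leaves non-index lesions out.

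**Denominator.** Section 7.2 divides complete plus partial responses by all evaluable patients, meaning eligible patients given at least two ipilimumab doses and SABR.

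**The concern.** A site that screens from Section 4 is never asked whether the patient has a measurable lesion. The patients this lets in are foreseeable. Sections 3.1.2 and 6.3.4 give SABR schedules for vertebral sites and a separate tier for brain metastases under 2 cm. A patient whose only disease is vertebral has no index lesion, and the same can happen when all lesions are small.

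Two secondary analyses are at stake. The response rate would include patients for whom one of the two response categories cannot be reached. PFS by irRC would include patients whose tumour progression cannot be judged by the SPD rule. Each reader would then have to decide how to classify them.

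**Working it through.** **1. The plan's own figure.** Section 7.1 uses 32 evaluable patients, a null rate of 15%, a target of 35%, and at least 8 successes. Exact binomial: P(X ≥ 8 | 32, 0.15) = 0.0958 and P(X ≥ 8 | 32, 0.35) = 0.918. Both meet the stated 10% error limits. Nothing below changes these figures.

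**2. From eligibility to a zero baseline.** Take a patient with one vertebral metastasis who otherwise qualifies.
- Section 4.1: eligible, with one site that SABR can target.
- Section 6.10.1: bone lesion, so non-measurable, so no index lesion.
- Baseline SPD is an empty sum, that is, 0.

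A patient whose lesions all fall below the size limits follows the same path.

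**3. Which categories survive.**
- mWHO PR: needs a 50% fall in index SPD (6.10.2). The non-index definitions offer only CR, SD and PD. Not computable.
- mWHO CR, SD, PD: defined for non-index lesions in 6.10.2. PD also follows from any new lesion (6.10.2 and Appendix III). The overall-response table has no row for a patient without an index assessment, but these categories can be read from the non-index definitions and Appendix III. Scorable.
- irCR: disappearance of all lesions, index and non-index (6.10.3). Scorable, although Table 11 pairs it with a -100% change that cannot be calculated.
- irPR, irPD and hence irSD: percentage change = (irSPD − reference SPD) / reference SPD. With a reference of 0, whether baseline or nadir, this is undefined.

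**4. Effect on irRC PFS.** If a new measurable lesion appears, irSPD goes from 0 to a positive value. One reader could call that irPD at once. Another could rely on the statement in 6.10.3 that new lesions alone are not progression. The first reading shortens irRC PFS and the second lengthens it.

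**5. Size of the effect on the response rate.** Let k be the number of the 32 with no index lesion, and p the response rate in the others. If none of the k has a CR, the reported rate is p × (32 − k)/32, a drop of p × k/32. The documents give no value for k; 3 and 6 are assumptions. For p, 11% is the ipilimumab rate in Section 1.2, 15.2% is the ipilimumab plus dacarbazine rate in Table 7, and 30% is an assumption.

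| p | k = 3 | k = 6 | Drop (points) |
|---|---|---|---|
| 11% | 0.11 × 29/32 = 10.0% | 0.11 × 26/32 = 8.9% | 1.0 to 2.1 |
| 15.2% | 0.152 × 29/32 = 13.8% | 0.152 × 26/32 = 12.4% | 1.4 to 2.9 |
| 30% | 0.30 × 29/32 = 27.2% | 0.30 × 26/32 = 24.4% | 2.8 to 5.6 |

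The share of patients without an SPD-based irRC assessment would be 3/32 = 9% to 6/32 = 19%.

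For scale, the approximate 95% half-width at n = 32 is 1.96 × √(p(1 − p)/32): 10.8 points at 11% and 15.9 points at 30%.

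**The case against.** The strongest reply is that measurability is in the protocol. The synopsis criterion and Section 4.1 can both be met, and this is a single centre where the principal investigator decides final eligibility (4.4). Baseline tumour measurements and index lesions are also presupposed at screening (6.5.1, 6.10.1). If the synopsis is enforced, the problem does not arise. That is correct. However, Section 4 is the list declared mandatory, and as written it admits patients whom the synopsis excludes, so the conflict remains.

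A reader might infer that response and irRC are wholly undefined for these patients, or that irRC PFS has no event for them. The documents do not support either. mWHO CR, SD and PD and irCR can be scored. Section 7.2 counts death as a PFS event. Section 6.10 also accepts biopsy and clinical evidence of progression alongside imaging. What is missing is the SPD-based progression event.

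A reader might also think the primary endpoint is compromised. It is not: mWHO progression can be established from non-index lesions or new lesions, and death is counted.

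It is fair to add that both affected endpoints are secondary, with no test or threshold attached, and that the response-rate shift is small beside the sampling error. Counting unscorable patients as non-responders is conservative for the response rate. It does not settle how to score irRC PFS.

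**Conclusion.** The contradiction is real and its effect is limited. Section 4 allows enrolment without measurable disease. For patients with no index lesion, mWHO PR and irPR, irSD and irPD cannot be computed, and those patients stay in the response-rate denominator. The primary 6-month PFS analysis and its decision rule stand.

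The number affected is unknown. The drops of about 1 to 3 points (at 11% to 15%) and 3 to 6 points (at 30%) rest on an assumed 3 to 6 patients and on none of them having a CR. They are illustrations, not estimates. Any CR among these patients would make the drop smaller.

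The difference between bone in the Study Summary and vertebral bodies in 4.1 might be read as the cause of the missing index lesions. It is not: 4.1 is the narrower list, and the gap comes from the omitted criterion together with 6.10.1. The site lists are a separate conflict. The treatment text divides in the same way (bone in the Study Summary and 6.1, vertebral in 3.1.2 and 6.3.4).

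**What to change.** Carry the synopsis criterion into Section 4.1: at least one measurable lesion as defined in 6.10.1. If patients without measurable disease are meant to be eligible, remove the criterion from the Study Summary and state in Section 7.2 that the response-rate and SPD-based irRC analyses are limited to patients with a baseline index lesion.

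Separately, reconcile the eligible-site lists in the Study Summary and 4.1.

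The cost is a wording amendment. Under the first option a few patients may be screened out; under the second, a few are left out of secondary denominators. The sample size and the primary analysis do not change.

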## **1.0 INTRODUCTION**

This document is a protocol for a human research study. This study is to be conducted according to US and international standards of Good Clinical Practice (FDA Title 21 part 312 and International Conference on Harmonization guidelines), applicable government regulations and Institutional research policies and procedures.

### **1.1 Specific Aims**

For nearly 30 years melanoma has been treated with chemotherapy agents like dacarbazine with a very modest benefit. A relative revolution in the treatment options for patients with metastatic melanoma has occurred over the last several years as promising targeted agents and immunotherapies have shown impressive disease stabilization rates. In order to turn impressive disease stabilization rates into actual long term disease control, additional therapeutic advances are needed. The immunotherapy agent ipilimumab is an exciting new agent which is being tested in a host of settings in melanoma to determine how to achieve a maximum benefit in disease control. We aim to improve the exciting advances in melanoma care afforded by ipilimumab by enhancing response rates and disease control with an aggressive local treatment like SABR (Stereotactic Ablative Radiation Therapy). This is important because overall response rates for melanoma immunotherapy remain low in metastatic disease and disease control rates stand at between 20 and 35% with overall survival measured in months.

The objectives of this study are:

